1.1 Background and Significance

The delivery of psychotherapy as it is currently designed is inaccessible to most patients in need of care, and is not provided as frequently as recommended, reducing its clinical impact. Advances in technology and ubiquitous ownership of mobile technology can be leveraged as novel methods of delivery to move the needle on rates of depression in the US.

Teletherapy is the use of mobile and communication technology to provide psychotherapy services at a distance. This is a method of psychotherapy delivery that has been in existence for nearly 40 years, originally as telephone-based care (1980's), then as videoconferencing-based care (2000's), and more recently as self-guided smartphone applications and internet programs and message-based (text and video messages) care. Research has consistently shown videoconferencing-based psychotherapy (VBP) to be an engaging form of delivery that enhances access equality, has high levels of patient satisfaction and is comparable to conventional treatment among diverse patient populations, ages and diagnostic groups. It is considered to be equivalent to and more accessible than traditionally delivered psychotherapy and is currently reimbursed under telehealth parity laws in as many as 36 states. However, many clinicians still harbor negative views of VBP, making access to this care limited. It is also delivered in the same way as in-person psychotherapy, with once-weekly meetings generally scheduled during the work week. Although transportation needs are mitigated, time demands are not. Thus, VBP, while effective, is challenged by a limited workforce and a limited therapeutic structure that is less engaging.

Message-based psychotherapy (MBP), defined as the use of text messages or asynchronous voice / video messaging, is an interesting alternative to VBP and self-guided psychotherapy (SGP). It differs from VBP in that patient-therapist contact can be done asynchronously, as often as needed, and like SGP, can be delivered when it matters most to the patient. However, like VBP, care is guided by licensed therapists who can intervene quickly

when a patient is struggling with a problem or needs more support and guidance with a therapeutic strategy. Studies show that asynchronous messaging between therapists and patients support action plan implementation, results in better therapeutic alliance and overall adherence to treatment recommendations by patients, and in small studies, results in significant reductions in depression. MBP is based on the theory that interventions have their biggest clinical impact when the consumer is at their greatest level of receptivity, and through better timing and tailoring, improve the consumers' readiness to change, self-efficacy to implement the intervention, and goal-directed behavior. MBP is becoming a widely available form of psychotherapy delivery, with as many as 20 companies providing MBP. MBP, like VBP, is reimbursable under some health plans, and small sample proof of concept studies found MBP to be engaging and effective, both alone and in combination with VBP.

MBP has yet to be rigorously evaluated for its effectiveness overall, and there is no guidance as to who should receive MBP alone or in combination with VBP. There is no research that has addressed when MBP should be offered alone or in conjunction with VBP, and who would respond (or not respond) to either alone or in combination. In sum, MBP may be the next, impactful, and novel method of psychotherapy delivery, but is in further need of study.

We propose that MBP may be a more potent intervention than weekly VBP alone because of (1) the frequency of contact between patients and therapists, (2) the relevance of therapeutic intervention at the time of its delivery, and as a result, (3) improved working alliance by patients.

This study will have commercial impact in that it will be the first to determine the relative effectiveness of unlimited, asynchronous MBP compared to more traditional VBP. Thus, this study will make a significant public health impact by being the first to evaluate a commercial product delivering MBP compared to VBP and addresses NIMH strategic priority area 4.1 (improve the efficiency and effectiveness of mental health services through research). Second, this study will have an impact on clinical care in that it will be able to determine the best digital treatment algorithm for people who do not respond to either MBP or VBP only and who respond to VBP, MBP, or the combination. There has been considerable interest in the clinical and policy realm in understanding who responds to different levels of care, and when patients should be "stepped up" in intervention intensity. Thus, this study will make a significant clinical impact by identifying a treatment sequence for systems that provide teletherapy and is responsive to NIMH priority area 3.2 (develop ways to tailor existing and new interventions to optimize outcomes).

1.2 Study Aims

This fast-track Small Business Innovations Research (SIBR) aims to (1) determine the relative effectiveness of unlimited MBP, compared to weekly VBP, (2) determine whether a switch to monthly VBP+MBP or weekly VBP+MBP is better for people who do not respond to VBP or MBP alone; (3) determine who responds to best to VBP, MBP, or the combined conditions, and (4) test the assumptions about the frequency and timeliness of treatment on working alliance and hence treatment outcomes.

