1.3 Study Description

In Phase 1, we will conduct a small randomized clinical trial to determine the best incentive model for retaining participants in a 12-week longitudinal sequential multiple assignment randomized trial (SMART)¹ trial. We will compare two incentive models (1) traditional, monetary incentive and (2) combination of low-monetary incentive and participant feedback. Participants will also be randomized to one of two treatment conditions: (1) MBP and (2) weekly VBP. Participants who do not respond to either modality alone will be re-randomized to receive combinations of MBP and VBP.

In Phase 2, we will conduct a large-scale clinical trial using a 12-week longitudinal SMART design to test the aims outlined in Section 1.2. We will aim to test the relative effectiveness of psychotherapy delivered via messaging-based platforms compared to video-based care, as well as determine the best method of enhancing care for those who do not respond to either daily messaging only or traditional, once-a-week video-based sessions.

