5.2 Study Assessments

Baseline Assessments:

- Demographics
- MDE Screener

- 9-item Patient Health Questionnaire (PHQ-9)
- 8-item Neuro-Quality of Life v1.0 (Neuro-QOL) Ability to Participate in Social Roles and Activities short form (Phase 2 only)
- 7-item Generalized Anxiety Scale (GAD-7)
- NIAAA Alcohol Screening Test
- IMPACT Assessment of Mania and Psychosis
- Self-reported health and health concerns
- Use of other apps and mental health treatment
- Participant Top Issue & Follow-Up Question (Phase 2 only)
- Perceived Stress Scale (Phase 2 only)
- Past Mental Health Treatment Experiences (Phase 2 only)
- Random Assignment Level 1 Reaction Questions (Phase 2 only)

Daily Assessments: Participants will be asked to answer brief, daily questions intended to capture information on daily fluctuations in mood, social and physical activity, and sleep.

Weekly Assessments:

- 9-item Patient Health Questionnaire (PHQ-9)
- 8-item Neuro-Quality of Life v1.0 (Neuro-QOL) Ability to Participate in Social Roles and Activities short form (Phase 2 only)
- 7-item Generalized Anxiety Scale (GAD-7)
- Patient Global Improvement Scale
- Major Life Event & Impact on Treatment (Phase 2 only)
- Participant Top Issue & Follow-Up Question (Phase 2 only)
- Therapist Contact Weekly Question

Week 1: Treatment Rationale Scale

Weeks 2 and 7: Credibility Expectancy Scale (Patient's Version) (Phase 2 only)

Weeks 4, 8, and 12:

- Major Life Changes
- Satisfaction with Care
- Perceived Stress scale (Phase 2 only)

Weeks 4 and 10:

- Experience of Care and Health Outcomes Survey (ECHO)
- Working Alliance Inventory-Short Revised (WAI-SR)

Week 12: Exit survey.

Early exit survey: Early drop out participants will be asked to complete a 1-question early exit survey (Phase 2 only).

Talkspace data: Talkspace meta-data (number of text interactions, time texting, time between texts, number of sessions) and content data including transcripts are collected on the Talkspace platform. All identifiable information (e.g., names, usernames, links) are scrubbed from the transcripts by an automated process internal to Talkspace prior to transfer to UW. Additionally, we will collect data on treatment intensity from Talkspace's electronic record of patient contact, which consists of time spent in treatment, number of sessions/messages over 12 weeks, and treatment attendance.

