1. Test effectiveness of unlimited daily, message-based psychotherapy (MBP) for depression, compared to weekly traditionally delivered, videoconferencing-based psychotherapy (VBP). Level 1 conditions: unlimited MBP and weekly VBP.
2. Develop an evidence-based treatment sequence for those who do not respond to either MBP or VBP. Level 2 conditions for participants who do not respond to treatment: MBP+VBP_{weekly} (switch from MBP to weekly VBP with MBP), MBP+VBP_{monthly} (switch from MBP to monthly VBP with MBP), VBP_{weekly}+MBP (switch from VBP to weekly VBP with MBP), and VBP_{monthly}+MBP (switch from VBP to monthly VBP with MBP).

Hypothesis 1: Compared to those randomized to weekly video care at baseline, patients randomized to message-based care will have greater improvements in depression (1a) and social functioning (1b), be more likely to show a treatment response (1c), and be more likely to experience remission (1d) at 5 and 12 weeks of care. Hypothesis 2: For those who fail to respond to treatment from baseline to 5 weeks, those re-randomized to receive (or retain) weekly video care will have greater improvements in depression and be more likely to show a response to treatment than those randomized to monthly video care. Hypothesis 3 (moderator): Baseline anxiety will moderate improvement in depression such that those with greater anxiety will have better response to message-based care at 5 and 12 weeks than to video-based care. Exploratory Aims: Exploratory evaluation of differences among groups in treatment engagement by week 5, ratings of therapeutic alliance at weeks 4 and 10, ratings of

quality of care and amount helped by treatment at week 10, and ratings of goal satisfaction, plans to continue using treatment, and likelihood to recommend treatment to others at week 12.

Sample Size and Power: We propose to screen 4,789 potential participants, anticipating we will enroll 1,250 participants to arrive at a final sample of 1,000 evaluated participants, assuming a 20% dropout rate by the last assessment. In our previous psychotherapy studies, dropout rates have been on the order of 10% by final assessment. In our recent on-line studies with Google Verily, drop out has been on the order of 20%. Our large incentive arm, tested in Phase 1, is based on the incentive analyses done on the Baseline Mood Study at Verily.

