Hypothesis	Timepoint(s)	Statistical Test	Contrast/analysis of interest
1a: Compared to those randomized to weekly video care at baseline, patients randomized to message-based care will have greater improvements in depression	Baseline to W5	3-level mixed effects model	MBP vs VBP
1b: Compared to those randomized to weekly video care at baseline, patients randomized to message-based care will have greater improvements in social functioning	Baseline to W12	3-level mixed effects model	MBP vs VBP
1c: Compared to those randomized to weekly video care at baseline, patients randomized to message-based care will be more likely to show a treatment response at 5 and 12 weeks of care.	Between W3 to W5 / W12	Chi-square tests	MBP vs VBP
1d: Compared to those randomized to weekly video care at baseline, patients randomized to message-based care will be more likely to experience remission at 5 and 12 weeks of care.	Between W3 to W5 / W12	Chi-square tests	MBP vs VBP
2: For those who fail to respond to treatment from baseline to 5 weeks, those re-randomized to receive (or retain) weekly video care will have greater improvements in depression than those randomized to monthly video care	W6 to W12	3-level mixed effects model with time centered at week 6	MBP+VBP _{weekly} vs MBP+VBP _{monthly} ; VBP _{weekly} +MBP vs VBP _{monthly} +MBP
2: For those who fail to respond to treatment from baseline to 5 weeks, those re-randomized to receive (or retain) weekly video care will be more likely to show a response to treatment than those randomized to monthly video care	W12	Chi-square test	MBP+VBP _{weekly} vs MBP+VBP _{monthly} ; VBP _{weekly} +MBP vs VBP _{monthly} +MBP
3 (moderator): Baseline anxiety will moderate improvement in depression such that those with greater anxiety will have better response to message-based care at 5 and 12 weeks than to video-based care.	Baseline to W12	3-level mixed effects model, with mean-centered baseline GAD-7	MBP vs VBP

Exploratory: We will explore whether there will be differences among groups in treatment engagement by week 5	Between W3 to W5	Chi-square test	MBP vs VBP
Exploratory: We will explore whether there will be differences among groups in ratings of therapeutic alliance	W4 / W10	2-level mixed effects models	W4: Level 1 conditions (MBP vs VBP); W10: Level 2 conditions (MBP vs VBP; MBP+VBP _{monthly} vs MBP+VBP _{weekly} ; VBP _{monthly} +MBP vs VBP _{monthly} +MBP)

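### Aim 4 promises to test whether contact frequency and timeliness act on outcome through working alliance, but the planned analyses only compare alliance between arms

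*Combined protocol and SAP*

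**What the plan says.** **Rationale and aim.** Section 1.1 argues that messaging may outperform weekly video because contact is more frequent and more timely, "and as a result, (3) improved working alliance by patients". Section 1.2 turns this into Aim 4, to "test the assumptions about the frequency and timeliness of treatment on working alliance and hence treatment outcomes". Section 1.3 describes Phase 2 as a "12-week longitudinal SMART design to test the aims outlined in Section 1.2".

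**Data.** Section 5.2 schedules the WAI-SR at weeks 4 and 10 and the PHQ-9 weekly. It also lists platform records of text counts, texting time, gaps between texts and sessions. Section 6.0 (Data Transfers) says these records are merged with the REDCap assessments before transfer for analysis.

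**Analysis.** Section 8.0 gives two Phase 2 goals and three hypotheses, none of which mentions alliance, contact frequency or timeliness. Alliance enters under the exploratory aims as "ratings of therapeutic alliance at weeks 4 and 10". The matching Table 2 row reads "We will explore whether there will be differences among groups in ratings of therapeutic alliance". It uses 2-level mixed models, with MBP against VBP at week 4 and Level 2 conditions at week 10.

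**The concern.** Aim 4 is a chain: contact frequency and timeliness change alliance, and alliance changes outcome. Testing it needs an analysis with measured contact as a predictor of alliance and one with alliance as a predictor of depression. The plan has neither.

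An arm difference in alliance at week 4 would not fill the gap. The Level 1 arms differ in medium as well as in how often and how promptly contact occurs, so the difference could not be credited to frequency or timeliness. It would also say nothing about whether alliance altered PHQ-9.

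At stake is what the trial can claim about why one mode of delivery works better, which is the argument of Section 1.1. If no analysis is specified in advance, any later statement about mechanism would be post hoc.

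**Working it through.** The documents give no sample size, effect size or power for Aim 4, so there is no figure to reproduce. The check sets the aim against the plan.

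**1. Aims against hypotheses**

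| Aim (Section 1.2) | Counterpart in Section 8.0 |
|---|---|
| 1. Messaging against weekly video | Hypotheses 1a to 1d |
| 2. Next step for non-responders | Hypothesis 2 |
| 3. Who responds to what | Hypothesis 3 (baseline anxiety as moderator) |
| 4. Frequency and timeliness, alliance, outcome | No hypothesis; one exploratory alliance row |

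**2. Rows of Table 2.** Ten rows are legible: 1a, 1b, 1c, 1d, two for Hypothesis 2, Hypothesis 3, engagement, alliance, and the week-12 ratings.
- Alliance appears in 1 of 10, as an outcome.
- Alliance as a predictor of PHQ-9, response or remission: 0 of 10.
- Talkspace contact records as a predictor: 0 of 10. The engagement row is a chi-square test of engagement between arms.

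The prose on models in Section 8.0 adds neither analysis. The week-10 ratings of care quality and amount helped, named among the exploratory aims, are also group comparisons.

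**3. What the alliance row can show**
- Week 4, MBP against VBP: a randomised estimate of arm on alliance, with frequency, timeliness and medium bundled together.
- Week 10, MBP starters, weekly against monthly video: a randomised estimate of scheduled video frequency on alliance, among non-responders to MBP.
- Week 10, VBP starters: printed as VBP_monthly+MBP against VBP_monthly+MBP, so there is no contrast as written. The week-12 ratings row gives weekly against monthly for the same group, which indicates the intended comparison.

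**4. Whether the schedule permits a proper test.** It does. Contact in weeks 1 to 3 precedes the week-4 WAI-SR. The week-4 WAI-SR precedes the week-5 PHQ-9. Section 8.0 places Level 2 assignment at week 6, after the week-5 score.

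**5. Whether the stated power covers it.** It does not. Assume two-sided alpha of 0.05 (none is stated) and 500 per arm. Level 1 power for 0.20 SD is Φ(0.20 × √(500/2) − 1.96) = Φ(1.20) = 88.5%, consistent with the stated figure of more than 80%. For an indirect effect, take a joint-significance test in which both links must be significant:
- Arm to alliance, effect a in SD: power = Φ(a × √(N/4) − 1.96)
- Alliance to outcome, partial correlation b: power = Φ(b / √((1 − b²)/N) − 1.96)
- Joint power = product of the two

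The values of a and b are assumptions. N = 800 is a pessimistic case in which a fifth of the 1,000 lack a needed rating.

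| a | b | N = 1,000 | N = 800 |
|---|---|---|---|
| 0.1 | 0.1 | 0.352 × 0.888 = 31% | 0.293 × 0.811 = 24% |
| 0.2 | 0.1 | 0.885 × 0.888 = 79% | 0.807 × 0.811 = 65% |
| 0.3 | 0.2 | 0.997 × 1.000 = 99.7% | 0.989 × 1.000 = 99% |

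This covers arm, alliance and outcome only, and ignores clinician clustering. Power runs from about 24% to 99.7% across plausible inputs, so the Level 1 figure cannot stand in for Aim 4.

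**The case against.** **The arms themselves carry contact frequency.** Level 1 sets unlimited messaging against weekly video, and Level 2 randomises non-responders to weekly or monthly video. A reader might infer that no row links frequency to alliance, or that the trial can say nothing about Aim 4. Neither inference is supported. The week-10 contrast among MBP starters is a randomised comparison of video frequency on alliance, and precise null results at weeks 4 and 10 would count against the chain. This part of the objection stands: the first link is partly informed. Measured contact and the link from alliance to outcome remain untested.

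**Phase 2 may have been meant more narrowly.** The sentence in Section 1.3 after the reference to the aims mentions only relative effectiveness and enhancing care, and Section 8.0 lists two goals. This shows that the inconsistency could be settled by narrowing Aim 4 instead of adding a model. It does not remove the inconsistency, because Section 1.3 refers to the Section 1.2 aims without exception.

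**The model may be described elsewhere.** Section 8.0 cites a separate protocol paper, which is not among the documents reviewed. It might contain a mediation analysis. The SAP and its Table 2 do not.

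**The stakes are modest.** Alliance is already exploratory, and the added analysis would be too. That is fair, and it limits the priority of the point.

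**Conclusion.** The point holds. Carried out exactly as written, the plan informs the link from arm to alliance. It leaves untested whether measured frequency or timeliness explains alliance, and whether alliance affects depression. One of four stated aims is affected. The change is worth making, but the primary comparison does not depend on it.

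A reader might also infer that the timing of measurements is a flaw, because early response is taken between weeks 3 and 5 while alliance is first rated at week 4. The documents do not support that as a defect: no planned analysis relates alliance to that response variable, and the week-4 WAI-SR precedes the week-5 PHQ-9. It is only a caution for anyone building the added analysis, since a week-3 score would come before the mediator and a week-4 score would coincide with it. Nor does the gap bias the tests of Hypotheses 1 to 3, none of which uses alliance.

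The conclusion rests on the Table 2 rows legible in the text, on Level 2 assignment falling at week 6 as Section 8.0 states, and on the cited protocol paper not supplying the missing analysis.

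**What to change.** Choose one of two routes.

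**Route A: add an exploratory Aim 4 row to Table 2.**
- Order: Level 1 arm; contact records from weeks 1 to 3; WAI-SR at week 4; PHQ-9 at week 5. Use completion dates to confirm the order, since weekly assessments have a 3-day window. Do not use the weeks 3 to 5 response variable or the week-6 PHQ-9, which coincides with Level 2 assignment.
- Keep clinician clustering, adjust for baseline PHQ-9, and state a rule for missing WAI-SR and contact data.
- Model response-time measures within arm where the other arm has no counterpart. Gaps between texts have no evident equivalent in weekly video.
- Treat week-3 PHQ-9 as a confounder that treatment may have affected. Ordinary adjustment can block part of the effect sought, so use a method that allows for this, such as interventional indirect effects, or show results with and without it.
- Add a sensitivity analysis for unmeasured mediator-outcome confounding.
- State that the week-10 comparison does not test mediation of Level 1 effects.

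**Route B: restate Aim 4** as an exploratory comparison of working alliance between conditions at weeks 4 and 10, and draw no conclusion about mechanism.

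**In either case,** correct the week-10 contrast that compares VBP_monthly+MBP with itself.

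**Cost.** Route B is wording only. Route A is SAP wording plus one analysis on data already scheduled. Its limits should be stated: it is observational beyond the randomised arm, has a one-week outcome window, and has no stated power.

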1.3 Study Description

In Phase 1, we will conduct a small randomized clinical trial to determine the best incentive model for retaining participants in a 12-week longitudinal sequential multiple assignment randomized trial (SMART)¹ trial. We will compare two incentive models (1) traditional, monetary incentive and (2) combination of low-monetary incentive and participant feedback. Participants will also be randomized to one of two treatment conditions: (1) MBP and (2) weekly VBP. Participants who do not respond to either modality alone will be re-randomized to receive combinations of MBP and VBP.

In Phase 2, we will conduct a large-scale clinical trial using a 12-week longitudinal SMART design to test the aims outlined in Section 1.2. We will aim to test the relative effectiveness of psychotherapy delivered via messaging-based platforms compared to video-based care, as well as determine the best method of enhancing care for those who do not respond to either daily messaging only or traditional, once-a-week video-based sessions.

